Topical lidocaine (0.5 grams of Lidocaine in LET gel) will be applied immediately after applying aloe gel (CONTROL) to the volar surface of the mid-forearm at two locations (right antecubital fossa and right wrist). Immediately after application of the aloe gel, the topical lidocaine (LET gel) will be applied. Immediately after the topical lidocaine (LET gel) is applied, pain will be assessed by the investigator every minute using the Pin-Prick Pain test. The time that the subject reports no pain (complete local anesthesia) will be recorded as the time to achieve anesthesia for the topical lidocaine without STAR particle application (T_{LET}) at both sites.

The physician will also evaluate local tolerability by assessing the topical lidocaine (LET gel) alone and topical lidocaine (LET gel) post-STAR particle application site for acute skin reactions (ASRs), AEs, and SAEs on the day of application, 1 hour [± 5 minutes] after the application, 24-hours after

Protocol Title: Rapid local anesthesia by lidocaine administered using STAR particles

application, one week after application, and 30 days after application. Specifically, the participant (and parent) will report if the participant’s skin has erythema, edema, blistering, tenderness, bleeding, bruising, or any type of skin change. ASRs will be scored quantitatively with qualitative remarks as needed. ASRs, AEs, and SAEs of interest will be recorded.

7. Data Specimen Banking

This study will not be banking any specimens or data.

8. Sharing of Results with Participants

There are no expected incidental findings for the study. Results will not be returned to the participant.

9. Study Timelines

- Each subject will participate in the study for the one visit with phone follow-up one day to 30 days after the study visit.
- The duration anticipated enrolling all study participants is 2-3 months.
- The estimated date for the investigators to complete this study (complete primary analyses) is 12 months.

Study Procedures and Assessments

Procedures and Assessments	Study Visit	Follow-Up (24-hrs – 30 days)
Informed consent	X	
Medical history	X	
Inclusion and exclusion criteria	X	
STAR & Lidocaine application by clinician	X	
topical lidocaine (LET gel) application by clinician	X	
TEWL measurement before and after application	X	
Application site pain by VAS	X	
Application site pain by report	X	
ASRs, SAEs & AEs of interest	X	X

10. Inclusion and Exclusion Criteria

Inclusion criteria:

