The risks to this study are minimal. We will be applying STAR particles that should puncture the skin, allowing the lidocaine to have more rapid entry and then, due to the elastic forces of the skin, will push the particles out. From the time the STAR particles are applied to the skin, the possible risks would be expected to be local skin reactions at the site of STAR particle application including erythema, edema, tenderness, bleeding, and/or bruising.

A systemic reaction would be unlikely to occur, but due to the potential that the application and retention of STAR particles in the skin could facilitate bacterial entry into the skin, in addition to the local reactions listed above, systemic reactions including: fever, cough, nausea, vomiting, diarrhea, fatigue, and headaches could also occur. Based on previous human research with STAR particles, local and systemic reactions are unlikely to occur (1). Acute skin reactions (ASRs) will be scored quantitatively with qualitative remarks as needed. The application of the STAR particles is expected to have a minimal risk to the subject. It is possible subjects could describe the placement of the STAR particles as uncomfortable or painful, but based on previous human studies (1) this seems less likely. We will take precautions to prevent infections, such as using sterilized or low bioburden materials and wiping the skin with an alcohol swab before the study.

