Based on previous clinical studies and FDA approvals of other drugs/devices using these materials, we therefore expect non-significant risk.

16. Potential Benefits to Participants

There is no direct benefit to the participant, however, there are potential future benefits to society from the understanding gained by the study.

17. Compensation to Participants

Study participants will receive \$100 for completion of the study visit. Participants who drive to the visit will be reimbursed for parking in the designated ECC parking area.

18. Data Management and Confidentiality

Data will be stored either electronically in HIPAA compliant locations or in locked offices and cabinets. The data will be stored locally until we are allowed by the sponsor or Emory to destroy them. Only staff directly involved in completing study procedures will have access to the data. Staff listed on the delegation of authority log will be responsible for receipt and transmission of data. The coordinator or PI/Sub-I will be responsible for transporting the data locally.

If a participant declines to participate *or is ineligible to participate for any or all portions* of the study, the participant will not be assigned a study ID number and the study staff will refrain from collecting any data on the participant.

19. Provisions to Monitor the Data to Ensure the Safety of Participants

As this study is one with minimal risk, a DSMB will not be needed.

Subject safety:

- Specific subject safety parameters: subjects will report any safety-related issues or concerns to the PI (phone/email when not at a visit) or in person to the PI when at the visit.
- Subjects will report observations when at the clinic for the initial visit, and will record observations to be made available to the research team when either contacting the research team or the research team contacting them.
- The PIs will be responsible for safety monitoring

Protocol Title: Rapid local anesthesia by lidocaine administered using STAR particles

- If the subject has skin irritation, pain, itching, or infection, a topical medication could be applied to address the symptoms.
- The minimal risk associated with STAR particles makes it unlikely that a subject would develop any significant local or systemic consequence and therefore, other than subject choice or PI choice, there is not expected to be any condition that should stop the study.
- Deviations, AEs, and SAEs will be reported to the IRB by the PI.

Data Integrity:

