
- Specific data elements to be reviewed include: pain (if any) associated with STAR particle formulation insertion, local skin findings at initial placement, and local skin findings during the study.
- Monitoring of data will occur every month after every 5 subjects are enrolled so that data will be monitored 4-5 times during the study depending on how quickly enrollment is complete.
- The PIs will be responsible for data monitoring

Additional considerations for FDA regulated trials

- All study activities except production of the STAR particles will be done on-site
- The study team will self-monitor the study
- The study team will use Emory University's self-monitoring tool found on the CTAC website
- The first subject enrolled will trigger a self-monitoring event
- No Identification of deviations or failures that would be critical to study integrity

20. Provisions to Protect the Privacy Interest of Participants

Whenever possible, a study number, rather than the participants name will be used on study records. The participants name and other identifying information will not appear when study results are presented or published. All study documents will be kept in a locked office or secure server.

The sponsor representatives and regulatory authorities (e.g., IRB, OHRP) may inspect all documents and records required to be maintained by the investigator. The study team will permit access to such records.

Subjects will be made aware that all research activities are completely voluntary and will not impact the care they receive. They will also be informed that they are allowed to withdraw from the study at any time.

The quantitative data from this study will be uploaded to the DDL or another repository within 30 days of the primary manuscript publication. A description of the data repository will be included in the informed consent.

21. Economic Burden to Participants

There will be no costs for the participant associated with the research study.

22. Informed Consent

- Participants will be consented by the Principal Investigator in a private space in the CHOA Endocrine clinic or the ECC.
- There is no standard waiting period before the participant is approached for consent after being told about the study.
- The participant will be reminded throughout the study visit that participation is completely voluntary and that they are allowed to withdraw at any point during the visit or after the visit.

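### The systemic reactions named in Section 15 are not itemised in the Section 6 follow-up questions or the Section 19 review elements, so non-serious ones are likely to be under-ascertained

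*Protocol*

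**What the plan says.** **Section 15 (Risk to Participants)** states that application and retention of the particles "could facilitate bacterial entry into the skin" and that, besides local reactions, "systemic reactions including: fever, cough, nausea, vomiting, diarrhea, fatigue, and headaches could also occur". It calls such reactions unlikely and describes precautions against infection.

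**Section 6 (Procedures Involved)** introduces the safety assessment with "The physician will also evaluate local tolerability by assessing" and applies it to the application sites for ASRs, AEs and SAEs. The time points are the day of application, 1 hour, 24 hours, one week and 30 days. It then specifies what the participant and parent report about the skin: "erythema, edema, blistering, tenderness, bleeding, bruising, or any type of skin change". It closes with "ASRs, AEs, and SAEs of interest will be recorded".

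**Section 9 (Study Timelines)** has a schedule row, "ASRs, SAEs & AEs of interest", marked at both the study visit and follow-up. Follow-up is by phone.

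**Section 19** has two relevant parts.
- Under Subject safety, subjects are to bring safety concerns of any kind to the principal investigator and to record observations for the team. The principal investigators monitor safety, and AEs and SAEs are reported to the IRB with no limiting qualifier. One bullet foresees local problems that may need attention: "If the subject has skin irritation, pain, itching, or infection".
- Under Data Integrity, the elements named for review are pain on application, "local skin findings at initial placement, and local skin findings during the study".

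**The concern.** The protocol's risk statement has a local half and a systemic half. The local half was turned into specific questions and review elements, and the systemic half was not. Follow-up is by phone, so what is asked largely determines what is found. A family may not connect a fever or diarrhea some days later with a gel rubbed on the forearm, and so may not raise it unprompted.

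If local reactions are solicited item by item and systemic ones are not, a report that only local reactions were seen would partly reflect the way the question was put. This matters more here because the study summary labels the trial a first-in-humans feasibility study, it enrols from age 10, it has no DSMB, and the principal investigators do both the safety and the data monitoring. With little outside oversight, the protocol wording carries much of the safeguard.

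**Working it through.** No sample size, power or event figure enters this point, so there is no formula to apply. The check is a comparison of lists.

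**Step 1. Reactions named in Section 15 against the two itemised lists.**

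| Named in Section 15 | On the Section 6 report list | Among the Section 19 review elements |
|---|---|---|
| Local: erythema, edema, tenderness, bleeding, bruising | 5 of 5 | Covered as local skin findings |
| Systemic: the seven symptoms quoted above | 0 of 7 | 0 of 7 |

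The Section 6 list has six named signs (the five above plus blistering) and a catch-all. The catch-all is itself confined to skin changes, so it cannot take in fever, cough, gastrointestinal symptoms, fatigue or headache.

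**Step 2. The local problems foreseen in Section 19 against the Section 6 list.** Irritation and visible infection at the site could be caught by the named signs or the catch-all, and pain partly by tenderness. Itching is a sensation rather than a visible change and is not clearly covered. Infection is not asked about by name.

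**Step 3. Other routes by which a systemic reaction could enter the record.**

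- *AE/SAE assessment at each time point (Section 6).* It exists, but it is framed as local tolerability and directed at the application sites. Inspecting or asking about a forearm site does not reveal a fever.
- *Recording of events of interest (Section 6 text and Section 9 row).* The qualifier is not defined or linked to the Section 15 list. Its reach is also ambiguous: in the schedule's word order, SAEs can be read as unrestricted and only AEs as limited.
- *Subjects' own recorded observations and reports (Section 19).* These are not confined to skin, and observations are passed on when the team makes the contact as well as when the subject does. They still depend on the family noticing the symptom and thinking it relevant.
- *Reporting to the IRB (Section 19).* This carries no qualifier. It operates on events already captured, so an event left unrecorded because it was not judged of interest may never reach it. The recording rule and the reporting rule do not match.

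**Step 4. Inference.** A serious systemic infection would probably surface through SAE capture. A non-serious systemic symptom has routes into the record but is prompted by no itemised question, while each named local reaction is prompted. Ascertainment is therefore uneven, in the direction of fewer systemic reports.

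**The case against.** The strongest reply is that capture already exists. AEs and SAEs are assessed at every time point, the schedule marks them at follow-up, subjects keep observations for the team, the principal investigators monitor safety, and AEs and SAEs go to the IRB. All of this stands. A reader might infer from the two lists that systemic reactions are never asked about or reviewed; the documents do not support that.

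Three further readings also go too far.
- *That the Section 19 list is the complete safety review.* It sits under Data Integrity, apart from the Subject safety provisions, and is worded as inclusive rather than exhaustive.
- *That bacterial entry is the most serious risk named.* Section 15 makes no such ranking and also names anaphylaxis.
- *That the follow-up calls use a closed questionnaire on which a systemic symptom could not be mentioned.* The protocol describes no such instrument.

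It can also be said that the stated endpoints are time to anesthesia and TEWL, so no formal safety endpoint is weakened. Systemic symptoms have no comparator, since each participant receives both applications. A case report form or safety plan not shown here may list these symptoms. The first two are fair limits on what the data could show, but they do not remove the reason to ask about reactions that the protocol itself names. The third is possible, but the protocol does itemise what is reported and leaves the systemic half out, so the wording that governs the study should be aligned.

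**Conclusion.** The point holds in a limited form. Of the seven systemic reactions in Section 15, none is among the items specifically asked of the participant or parent in Section 6, and none is among the data elements named for review in Section 19. They rest on a site-based AE/SAE assessment, an undefined category of events of interest, subjects' own observations and reports, and general IRB reporting. Non-serious systemic reactions are likely to be under-ascertained relative to local ones in the 25 participants.

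The size of the under-ascertainment cannot be estimated from the documents. No count of affected contacts is offered either, because the places that describe follow-up differ: the Section 1 summary lists phone calls at 1 week and 4 weeks only, while Section 6 has assessments at 24 hours, one week and 30 days. The conclusion assumes that unprompted symptoms are reported less completely than prompted ones, and that no document outside the protocol already lists them. It is a change that should be made, and it does not touch the efficacy comparison.

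**What to change.** 1. **Section 6, report list.** Add the systemic reactions named in Section 15, plus itching and signs of infection at the site, to what is asked at each existing follow-up contact.
2. **Section 6 text and Section 9 schedule row.** Replace the limit to events of interest with all AEs and SAEs, so that recording matches the unrestricted IRB reporting line in Section 19.
3. **Section 19, Data Integrity.** Add systemic reactions and signs of infection to the elements named for review.

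The cost is protocol wording and slightly longer calls, with no new visits or contacts. The downside is that some unrelated background symptoms will be recorded. Because each participant receives both applications, these cannot be attributed to one arm and should be reported per participant.

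### Section 19 leaves any safety pause to PI discretion, and the adults-first step in Section 10 requires no observation before the first minor is treated

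*Protocol*

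**What the plan says.** The protocol has several safety provisions.

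- **Stopping (Section 19, Subject safety).** After a statement that risk is minimal, the text says that "other than subject choice or PI choice, there is not expected to be any condition that should stop the study".
- **Oversight (Section 19).** "As this study is one with minimal risk, a DSMB will not be needed". The PIs are responsible for safety monitoring.
- **Reporting (Section 19).** Outside the visit, by phone or email, as well as at the visit, "subjects will report any safety-related issues or concerns to the PI". Further, "Deviations, AEs, and SAEs will be reported to the IRB by the PI".
- **Response to a local problem (Section 19).** "If the subject has skin irritation, pain, itching, or infection, a topical medication could be applied to address the symptoms".
- **Reviews (Section 19).** "The first subject enrolled will trigger a self-monitoring event", and "Monitoring of data will occur every month after every 5 subjects are enrolled", giving 4-5 reviews in all. The data elements listed for review are application pain and local skin findings.
- **Assessments (Section 6).** The physician checks for "acute skin reactions (ASRs), AEs, and SAEs on the day of application", and again at 1 hour, 24 hours, one week and 30 days.
- **Order of enrolment (Section 10).** The first two participants are aged 18-21. No interval or condition separates them from the first participant under 18; the lower age limit is 10.
- **Foreseen risks (Section 15).** Bacterial entry through the treated skin, systemic reactions, allergic reaction and anaphylaxis are named as possible. Sterilized or low-bioburden materials and an alcohol wipe are the stated precautions. Earlier human use of the particles is reported to have shown only transient local erythema.

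**The concern.** Two things are left open.

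First, the adults-first step has no content beyond sequence. Treating two young adults before any child is useful only if something is learned from them first. A team could treat both adults and a 10-year-old on the same day and still comply with Section 10.

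Second, the provisions in Sections 6 and 19 detect events and report them, but none says that the next application waits. If a related infection came from the materials, the next participant might receive the same materials. The participants are healthy, most may be minors, and Section 16 says that they get no direct benefit. A consistent, recorded pause for the few events that the protocol itself foresees would be a reasonable minimum.

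**Working it through.** **Step 1: does any provision hold the next application?**

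| Provision | What it does | Pause for the next participant? |
|---|---|---|
| Checks on the day, at 1 h, 24 h, one week, 30 days (Section 6) | Finds events | None stated |
| Direct reports to the PI (Section 19) | Informs the PI | Only if the PI chooses |
| AE/SAE reports to the IRB (Section 19) | Informs the IRB; no timing given | None stated |
| Topical treatment (Section 19) | Optional care of the affected subject | None stated |
| First-subject self-monitoring (Section 19) | One check by the study team | None stated |
| Reviews every five subjects (Section 19) | Looks at pain and local skin findings | None stated |
| Two adults first (Section 10) | Sets the order | None stated |

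**Step 2: reproduce the protocol's own figure.** Reviews every five subjects in 25 participants: 25 / 5 = 5, of which 4 come before the last block is complete. This matches the stated 4-5.

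**Step 3: pace.** Inputs are 25 participants (Section 12) and 2-3 months to enrol (Section 9). Even enrolment and 30.4-day months are assumptions, so enrolment lasts 60.8 to 91.2 days.

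- Participants per week: 25 / 60.8 × 7 = 2.9; 25 / 91.2 × 7 = 1.9.
- Days to enrol five: 5 × 60.8 / 25 = 12.2; 5 × 91.2 / 25 = 18.2.

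So about 1.9 to 2.9 further participants, any of whom may be a minor, could be treated between the second adult's visit and that adult's one-week contact. Blocks of five are about 12 to 18 days apart, and up to four more participants could be treated between an event and the next such review. The periodic reviews therefore cannot serve as a hold.

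**Step 4: cost of waiting one week after the second adult.** As a share of enrolment: 7 / 60.8 = 11.5%; 7 / 91.2 = 7.7%. This applies if no other 18-21-year-old is treated during that week.

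**Step 5: what cannot be computed.** The protocol gives no rate for related SAEs, systemic allergic reactions or infections. It calls systemic reactions unlikely and allergy to the aloe gel extremely rare. The chance that a pause would ever be triggered is therefore not estimated here.

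**The case against.** The strongest reply is that this is a deliberate choice with reasons given. The exposure is one visit with a topical product, the materials are in common use, and earlier human use showed only transient erythema. The quoted sentence is a forecast that keeps PI choice as a ground for stopping. The PIs receive reports directly, are responsible for safety monitoring, and, with the other investigators, perform all procedures (Section 23). A PI who learned of a related infection or anaphylaxis would very probably pause without being told to. Under a written rule the same PIs would still judge relatedness and release the pause, so no independent judgement is added. All of this stands, and it keeps the point small.

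A reader might infer that a child could be treated after an event known to be related before anyone had looked at it. The documents do not support that. An event known to be related has already been judged by someone, and reports go straight to the people who can stop the study. What is missing is a required, recorded review, not the possibility of one.

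A reader might also take the first-in-humans label in Section 1 to mean that the particles are untested in people. Sections 4, 14 and 15 refer to earlier human use.

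A further objection is that two event-free adults say little about rare events. That is true. The gate does not establish safety; it ensures that a problem in either adult would be seen before a child is treated. Finally, institutional and IRB procedures are not shown, so the point is only that this protocol contains no hold, not that none would operate.

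**Conclusion.** The point holds as a modest design improvement. The adults-first step requires no observation, and no provision ties a foreseen related event to a pause. The protocol does not contradict itself, and the existing checks and reporting routes are real.

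The measurable size is the 2 to 3 participants per week in the working, which rests on the stated enrolment plan and on even enrolment. The safety benefit cannot be put as a number, because the documents give no event rate; given the reported experience, the pause may never be used. The gate before minors is the firmer half, since it gives purpose to a step already in the protocol whatever the event rate. Neither part protects participants already treated.

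**What to change.** In the Subject safety list of Section 19, replace the sentence that expects no stopping condition with:

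> *Further applications pause after any of the following that a PI judges possibly related to the study application: an SAE; a systemic allergic reaction or anaphylaxis; an infection. They resume once the PIs have recorded a review of the event, including the materials used, and reported it to the IRB. Erythema and other mild local reactions, including mild local allergic reactions, do not trigger a pause. No participant under 18 will be treated until the first two participants (aged 18-21) have completed their one-week contact and the PIs have recorded that no trigger occurred or that its review is complete. If a one-week contact is missed, the next successful contact counts, or another 18-21-year-old replaces that participant. Subjects and PIs may still stop at any time.*

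This needs an amendment of a few sentences. It uses the one-week contact already in Sections 1 and 6, and adds no visit, staff or committee. The costs are about one week's wait after the second adult (roughly 8-12% of enrolment, less if other 18-21-year-olds are treated meanwhile, longer if a contact is missed) and a short pause if a trigger occurs.
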